UNIVERSITY OF MIAMI
MILLER SCHOOL
of MEDICINE

**IRB # 20130751
NCT02663817**

DMH-Based Plan Evaluation and Inverse Optimization in Radiotherapy

PRINCIPAL INVESTIGATOR:

[name].
Associate Professor
Department of Radiation Oncology
[name]
[name]
[contact]
[contact]
Email: [contact]

[figure not shown]
VERSION #: 4

VERSION DATE: 06 June 2017

TABLE OF CONTENTS

[figure not shown]
SCHEMA 3DCT, IMRT, VMAT:	3
SCHEMA SBRT:	4
HYPOTHESES:	5
1.0 BACKGROUND	5
1.1 Study Disease	5
1.2 Rationale	5
1.3 Gender and Ethnicity	10
2.0 STUDY OBJECTIVES	10
2.1 Primary objectives	10
2.2 Secondary objectives	10
3.0 PATIENT SELECTION	10
3.1 Inclusion Criteria	10
3.2 Exclusion Criteria	11
3.3 Enrollment and Withdrawal	11
4.0 RESEARCH PLAN	11
4.1 Assessment of Protocol Eligibility and Enrollment	11
4.2 Treatment Planning for Therapy Purposes	12
4.3 CT Exam Specifications	12
4.4 Other Imaging Studies	13
4.5 Experimental Virtual Treatment Planning	13
4.6 Duration of Study	14
5.0 DOSE MODIFICATIONS	14
6.0 DATA ANALYSES PLAN	14
7.0 DATA AND SAFETY MONITORING PLAN	15
8.0 HUMAN SUBJECTS INSTRUCTIONS	15
9.0 CRITERIA FOR DISCONTINUATION	19
10.0 DATA REPORTING	19
11.0 INVESTIGATOR'S RESPONSIBILITIES	19
APPENDIX I:	31
TABLE 1: STANDARD FRACTIONATION CALENDAR	31
TABLE 2: SBRT CALENDAR	31

SCHEMA 3DCT, IMRT, VMAT:

**CT = computed tomography; MRI = magnetic resonance imaging;
PET-CT = positron emission tomography; 3DCT = three-dimensional conformal radiotherapy; IMRT= Intensity Modulated Radiotherapy; VMAT = Volumetric Modulated Arc Therapy; CT = Computed Tomography Imaging; OARs = Organs at Risk;**

SCHEMA SBRT:

SBRT = Stereotactic Body Radiotherapy; CT = Computed Tomography Imaging; OARs = Organs at Risk;

HYPOTHESES:

- Mass-based inverse optimization in radiotherapy treatment planning will result in a reduction of normal tissue and organs at risk (OAR) doses for desired prescription therapeutic doses to the targets.
- Dose-mass histograms (DMHs) may be more relevant to radiotherapy treatment planning and treatment plan assessment than the standard of care, realized through dose-volume histograms (DVHs)

1.0 BACKGROUND

1.1 Study Disease

Lung cancer is the third most commonly occurring non-cutaneous cancer in the USA where the estimated number of new cases in 2013 was 228,190. Worldwide, it is the leading cancer in both incidence (1.61 million new cases annually) and mortality, (1.35 million deaths annually). In the USA alone lung cancer kills approximately 160,000 individuals yearly – more people than breast, colon and prostate cancers combined.¹⁻³ The 5-year actuarial survival estimate for non-small cell lung cancer (NSCLC) is approximately 15% for stages III-IV, and better for stages I-II. It has been shown that local disease control, using conventionally fractionated dose regimens, has not improved in more than a decade.⁴⁻¹⁴

Approximately 53,000 new cases of head and neck cancers [mostly squamous cell carcinoma (HNSCC)] are diagnosed in the United States each year. About two thirds of those cases present with a locally advanced disease. HNSCC patients comprise another challenging therapeutic category.¹⁵⁻²⁸

Prostate cancer is the most commonly occurring non-cutaneous cancer in the USA with a reported incidence of about 238,000 new cases each year. Despite advances in early diagnosis and in treatment, its cure remains elusive. Local persistence of prostate cancer treated with radiation therapy is under-appreciated. Prostate cancer has a long natural history and persistent disease may not be realized for many years.²⁹⁻³⁸

1.2 Rationale

1.2.1 Standard of Care in Radiotherapy

Lung cancer is the most common cause of cancer-related deaths. The prevalent histological types are non-small cell (NSCLC) and small-cell (SCLC) lung carcinomas. Treatment options include surgery, chemotherapy, and radiotherapy. It has been demonstrated that radiotherapy dose of 70 Gy is a significant threshold in terms of survival benefits for NSCLC, while doses of ~85 Gy are required to achieve 30 months of local progression-free survival. Phase I RTOG 0117 trial demonstrated that 74 Gy is the maximum tolerated dose in combined chemo-radiotherapy for that disease, indicating the detrimental effects of chemoradiotherapy which prohibit dose escalation. Single institution studies have reported on an improved local control with higher dose levels and/or higher doses per fraction, indicating that patients might benefit from radiotherapy dose escalation, realized by treatment planning and/or delivery techniques which minimize radiation doses to surrounding anatomical organs. In other words, if a technique which minimizes radiation dose to healthy tissue is developed, it will allow dose escalation (not to exceed an accepted level of healthy tissue toxicity) which might improve patient outcomes. Healthy tissue tolerance is very often the dose limiting factor for a successful definitive treatment. Symptomatic radiation-induced lung injury (RILI) occurs in ~30% of the patients, while radiologic evidence for RILI occurs in ~50% of the NSCLC cases. Radiographic changes in lung (as function of regional dose) have almost linear relation with dose across the therapeutic range. Lung toxicity has been correlated with both mean lung dose (MLD) and local doses. Published data indicates that the rate of radiation pneumonitis (RP) is dependent on MLD and volume indices ranging from V5 to V30. The abovementioned data suggest that new strategies for a potential dose escalation, through innovative treatment planning and delivery techniques, where lower radiation doses are delivered to healthy tissue, need to be explored.^{10, 12, 14, 34, 39-91}

Another challenging group of cancer patients includes head-and-neck squamous cell carcinoma (HNSCC) cases. Radiotherapy combined with concurrent chemotherapy is commonly used for treatment of stages III-IV of these cancers (category 1 level of evidence in the recommendations of the National Comprehensive Cancer Network Head and Neck Panel). Although various meta-analyses have clearly shown that delivering chemotherapy and radiotherapy concomitantly (chemoradiation) significantly boosts the effects of radiation alone, this approach raises a number of practical challenges, most of them resulting from poor treatment tolerance and reduced compliance to the prescribed dose levels of chemoradiation. Most HNSCC patients, receiving high-dose radiotherapy, are affected by severe acute side effects, including mucositis (stomatitis), dysphagia, and skin toxicity (radiation dermatitis). Chemoradiation is

associated with an even higher incidence of severe (grade 3/4) acute adverse events, indicating again the detrimental effects of chemo-radiotherapy combination for this treatment site. Although it has been repeatedly substantiated that combining radiotherapy with cisplatin and sometimes 5-FU yielded the best overall survival data, it can be claimed that the therapeutic potential of these drugs has been taken to its limit. An important avenue of research refers to advances in radiotherapy planning and delivery and, in particular, intensity-modulated radiotherapy (IMRT). Compared with conventional techniques IMRT allows better sparing of unaffected tissues. The subsequent reduction in radiation-induced mucositis and xerostomia may help to decrease the morbidity of intensive concomitant chemoradiotherapy.^{16, 17, 19, 20, 22-25, 92-98}

Radical prostatectomy and radiotherapy are both viable treatment options for clinically localized prostate cancer. Both modalities have evolved over time, such that to maximize cancer-free survival, while minimizing health-related risks like urinary incontinence, bowel incontinence, and sexual dysfunction. However, to date there is still not one superior single treatment that is devoid of side effects. Notably, three recent randomized trials have shown a consistent improvement in biochemical failure when adjuvant radiotherapy is administered with prostatectomy. However, the price to be paid for the increased control is the increased risk for complications and side effects in the radiotherapy arm by a factor of two. Over the past decade, many publications have shown that high dose IMRT represents optimal form of external beam radiotherapy for localized prostate cancer. The combination of IMRT with image guidance has allowed an enhanced target precision together with the accompanying reduction in clinical target volumes and even perhaps reduction in the treatment related toxicity. Therefore, development and incorporation into clinical practices of novel advanced radiotherapy planning and delivery techniques will permit us to deliver radiation more safely and reduce treatment duration significantly for thousands of patients.^{29-33, 36, 38, 99-118}

Approximately 60% of all cancer patients require radiotherapy for local tumor control. Quite often radiotherapy is combined with other treatment modalities such as chemotherapy. The current state of the art radiotherapy treatment planning and treatment plan evaluation relies on the DVH paradigm, where doses to volumes of target and normal anatomical structures are employed. Recently however, it has been argued that the effects of delivered radiotherapy dose seem to be more closely related to healthy tissue toxicity (and thereby to clinical outcomes) when dose-mass-histograms (DMHs) are considered in treatment plan evaluation.¹¹⁹⁻¹²¹ So far, mass information has been utilized only

in evaluation of treatment plans and radiobiological modeling for NSCLC. DMHs were introduced for evaluation and review of thoracic treatment plans. Shortly thereafter, the analytic rationale for their application was outlined. Investigation of the difference between DVHs and DMHs and their effects on the treatment outcomes showed that the deviation range between them is large. It was concluded that “*the effectiveness of the dose distribution delivered to the patients seems to be more closely related to the radiation effects when using the DMH concept*”. An example figure from Mavroidis *et. al.*, elucidating the grounds for that statement, is presented below.

[figure not shown]

Figure 3. The mean cumulative dose–volume histograms of the PTV and spinal cord show that the difference between the DVH and DMH is negligible. However, the difference of the two concepts appears to be significantly large for the lung.

The figure presents DVH and DMH analyses for a breast patient treated with radiotherapy. The authors state that “*it is shown that the DMH is lower than the corresponding DVH meaning that the lung actually receives a lower dose than what the DVH indicates. By interpreting these figures in terms of tissue response, it was found that the probability for lung complications was changed by 30% of its initial value closer to the clinically observed response rate*”

To date no investigation utilizing tissue mass (or density) effects explicitly in IMRT optimization process has been undertaken. We have incorporated mass directly in the cost functions for inverse planning, and will study its potential for doses reduction to healthy tissue and the magnitude of the potentially achievable isotoxic dose escalation. For the first time tissue mass information is used for

treatment planning purposes, rather than academic plan review: that is, a shift from DVH- to a new, DMH-based, treatment planning paradigm. We will also look into the use of tissue density incorporation in the cost function, and optimize dose to density rather than dose to volume. Furthermore, we will study global energy minimization (as a fundamental physical principal) and its place in inverse optimization, since it can be readily incorporated in the development of the proposed novel treatment planning framework. From a conceptual stand point there is no difference between mass-based and volume based optimization cost functions when media with constant density is considered. However, human body comprises many different tissues which vastly differ in density, from air cavities to bones. Under those conditions the mathematical representation of the mass-based optimization is more general than the representation of volume-based optimization. In other words, volume-based optimization is a special case of mass-based optimization in a media with a constant density. Therefore, we hypothesize, that applying the more general model (utilized through mass-based optimization) will be advantageous in certain situations and we want to explore what those situations are.^{32, 33, 42, 67, 73, 119-126}

1.2.2. Volumetric Imaging for Radiotherapy

All patients receiving radiation therapy undergo a high resolution CT scan, which is a fundamental step in the current clinical radiotherapy planning process. Recently it has become a standard of care to also include complementary imaging modalities such as magnetic resonance imaging (MRI) and/or positron emission tomography (PET-CT), which helps delineate tumors and normal tissue. In addition, it has become quite common to perform MRI and/or PET-CT studies on follow-up visits after radiotherapy course completion in order to assess treatment outcome.

1.2.3. Treatment Planning for Radiotherapy

Cancer patients are treated according to the standard of care with either conformal radiotherapy (3DCRT), intensity modulated radiotherapy (IMRT), volumetric modulated arc therapy (VMAT), or a linear accelerator (linac) based stereotactic radiation therapy (SRT). Treatment planning is performed with any combination of coplanar or non-coplanar fields to deliver the prescribed dose, while restricting the dose to the normal tissues to empirically determined dose levels. Field arrangements and plan parameter optimization are determined by

experienced planners to produce the optimal plan in accordance with volume definitions and attending physician prescriptions and goals.^{86, 127-137}

1.3 Gender and Ethnicity

It is estimated that the patient population who received radiation therapy at UMHC between 01/01/2003 and 12/31/2012 consists of 46% White, 10% African American, 42% Hispanic, and 2% Other.

2.0 STUDY OBJECTIVES

2.1 Primary objectives

- To study and evaluate whether DMHs are better suited for predicting radiotherapy response and/or complication (toxicity) than standard of care realized through DVHs.
- To investigate the time-trending changes between patient anatomy and DMH inverse radiotherapy optimization.

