4.2 Treatment Planning for Therapy Purposes

This protocol is a non-therapeutic protocol. Therefore, patients enrolled in this protocol will be treated according to the standard of care for IMRT, VMAT, and SRT.^{29, 97, 138-144} Treatment planning will be performed with any combination of coplanar or non-coplanar IMRT fields or VMAT fields, to deliver the specified dose while restricting the dose to the normal tissues. Field arrangements will be determined to produce the optimal plan in accordance with volume definitions. The treatment plan used for each patient will be based on analyses of the volumetric dose, including DVH analyses of the planning target volumes (PTVs) and critical normal structures, as well as evaluation of isodose curves and isodose volumes. In addition to the abovementioned analyses (which is according current standard of care) our study will evaluate the pertinent DMHs and isomass volumes for all anatomical structures of interest.

In addition to the planning CT scan and/or pre- and post-treatment MRIs and/or PET-CTs done routinely as part of standard of care, patients enrolled in this protocol will undergo two additional CT imaging studies at different times during the treatment course. CT studies are the primary data source for any type of external beam treatment planning. The information gained from the repetitive CT scans will be used to quantify the volumetric and mass changes of soft tissue (e.g. tumor shrinkage). Furthermore, the data will be used to assess the relation among soft tissue changes and radiographic features as well as dose-mass and dose-volume histograms, as well as the time-trends for DVHs and DMHs.

All head-and-neck patients will be immobilized using custom-fabricated thermoplastic face masks affixed to the couch. Lung and prostate patients would be immobilized in body immobilization bags such as Alpha Cradles and vacuum immobilization bags (or vac-bags). Patients will be immobilized in the intended treatment position and imaged with a CT scanner in the same way as for standard 3DCRT and IMRT/VMAT/SRT treatment planning. The final decision for treatment immobilization devices will be left to the discretion of the attending physician.

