4.5 Experimental Virtual Treatment Planning

The CT data acquired under this protocol will also be used for testing and development of our mass-based optimization methods. Those experimental plans will not be used for patient treatments. The plans used for patient treatment would be based on the standard of care described in section 4.3. Prospective data collection of 3D and 4D CT patient scans will be utilized for tallying DVH and DMH end-points and their relation to changes in pulmonary function, as well as studying interaction between tumor time-trending changes and DMH parameters in NSCLC, HNSCC, and prostate cases. All experimental mass-based treatment planning will be necessarily retrospective. Should a finding on one of the repetitive CT scans necessitate a change in plan or medical intervention, this will be at the discretion of the attending physician and will be performed according to the standard of care.

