6.0 DATA ANALYSES PLAN

This clinical imaging study will form a database for future research and development of 3D and 4D treatment planning approaches for different anatomical sites treated with radiotherapy. Statistical analyses will be used to assess the differences among standard of care, realized through DVHs, and our newly proposed mass-based optimizations and DMH evaluations. Those statistical analyses are powered to detect clinically significant differences in dosimetry and estimated clinical outcome endpoints between various proposed simulated treatment techniques. Significant changes include:

- Dosimetric: a dose variation between the different treatment planning approaches for normal tissue structures of more than 7%.
- Estimated clinical outcome: a $\geq 5\%$ variation of normal tissue toxicity using the generalized equivalent uniform dose (gEUD) metric and isoeffect parameters and analyses tools developed by the NCI funded R01 CA163370 research grant.

We will start with the null hypothesis that no difference between the treatment planning approaches is observed for the dosimetric and the estimated clinical outcome endpoints. Since patients are treated according to the standard of care and only their imaging information is used to estimate the potential outcome benefit of the new planning approaches, each patient serves as a control for themselves. Results will therefore be paired. The differences between the standard of care inverse optimization

and the proposed mass-based schemes for tumors will be tested using one-tailed paired *t*-tests, against a hypothesis that $\pm 3\%$ radiation dose differences in the tumors will not have an observable clinical significance. The differences between the optimization results on the remaining parameters for all healthy anatomical structures (within the radiation field) will be tested using standard two-tailed *t*-tests with the null hypothesis set to 0%. We anticipate an enrollment period of five years.

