8.2 RESEARCH MATERIAL

Along with the CT imaging studies and the physical description of the radiotherapy, the following data will be collected as well from each subject:

MRI studies (if any)	Toxicities
PET-CT studies (if any)	Prior Surgery
Age	Tumor location
Performance status	Diagnostic CT/MRI/PET report
Histology	Tumor volume
Disease stage	Medication
Patient weight	Critical structures

All of the data recorded will be entered into a database maintained by the principal investigator. Majority of that data for each patient is part of either our “record and verify” system or UChart. This data includes patient age, performance, histology, disease stage, patient weight, prior surgery, diagnostic report, medication. It will be

transcribed either by the PI or the study staff. For toxicity we will use CTCAE 4.0 grading system (cf. Appendix II). Tumor volume and location as well as volumes and locations for all adjacent healthy anatomical structures within the radiation field would be determined from the radiotherapy treatment plans used for patient therapy.

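### Neither test family in section 6.0 uses an observed outcome, so the stated tests cannot show whether DMHs predict response or toxicity better than DVHs (first primary objective)

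*Combined protocol and SAP*

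**What the plan says.** The first primary objective in section 2.1 reads: "To study and evaluate whether DMHs are better suited for predicting radiotherapy response and/or complication (toxicity) than standard of care realized through DVHs".

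Section 6.0 starts from "the null hypothesis that no difference between the treatment planning approaches is observed for the dosimetric and the estimated clinical outcome endpoints" and names two test families:

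- Tumors: one-tailed paired t-tests of standard against mass-based optimization, with a 3% dose margin.
- Healthy structures: two-tailed t-tests on the optimization results, with a null of 0%.

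The differences that count are a normal-tissue dose difference above 7% and a toxicity difference of at least 5%, the latter calculated through gEUD. Each patient is their own control because treatment follows standard of care and "only their imaging information is used to estimate the potential outcome benefit of the new planning approaches".

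Outcome-related material appears in other sections:

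- Section 4.2 would use the repeat scans to "assess the relation among soft tissue changes and radiographic features as well as dose-mass and dose-volume histograms".
- Section 4.4 collects other imaging, including MRI and PET-CT that physicians may order after treatment to judge response and complications.
- Section 4.5 says that "CT patient scans will be utilized for tallying DVH and DMH end-points and their relation to changes in pulmonary function", and adds "studying interaction between tumor time-trending changes and DMH parameters in NSCLC, HNSCC, and prostate cases".
- Section 8.2 states: "For toxicity we will use CTCAE 4.0 grading system".
- Section 10.0 stores TCP and NTCP calculations, both histograms, gEUDs, mgEUDs and physicians' follow-up reports.

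**The concern.** To ask whether one histogram predicts better than another, an analysis needs two predictors taken from the same treatment and an outcome to predict. Section 6.0 contrasts two plans instead, and its only outcome is a modelled one. If it is followed exactly, the study can report that mass-based planning changes dose or estimated toxicity and still be silent on its first primary objective.

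The protocol's own case for DMH uses a different yardstick. Section 1.2.1 cites a study in which "the probability for lung complications was changed by 30% of its initial value closer to the clinically observed response rate". That is a comparison of predicted with observed, and section 6.0 contains none.

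An outcome analysis added later would have to choose among three sites, many structures, several toxicity grades, and response or toxicity. If those choices follow sight of the data, the DMH-versus-DVH comparison is open to selection.

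**Working it through.** There is no stated figure to reproduce. The main check is of which variables enter each test.

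**1. Inputs to the tests.** For patient i, let x be a dose or a gEUD-based toxicity estimate, and let d_i = x_i(mass-based plan) − x_i(standard plan). Each paired test has the form

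t = (mean of d − δ0) / (s_d / √n),

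with δ0 = 0 for healthy structures and a 3% bound for tumors.

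| Family | Compared | Scale | Observed outcome used |
|---|---|---|---|
| Tumors | standard vs mass-based plan | dose | no |
| Healthy structures | standard vs mass-based plan | dose or gEUD-estimated toxicity | no |

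Count: 0 of 2.

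**2. Consequence.** Let Y_i be the observed toxicity or response. Y does not appear in t. Shuffle the Y values among patients: every t-statistic stays the same, while the association of Y with a DVH or DMH metric can become anything. This holds for paired and unpaired versions. It also holds on a wider reading of section 6.0's mention of DMH evaluations, with d_i = DMH metric − DVH metric, because Y is still absent.

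**3. Which plan can be linked to an outcome.** Sections 4.2 and 4.5 say that patients receive the standard-of-care plan and that experimental plans are never delivered. An observed outcome therefore exists only under the delivered plan. Objective 1 needs the DVH and the DMH of that one plan; section 6.0 contrasts two different plans.

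**4. The other sections.** Sections 4.2 and 4.5 set both histograms against an observed change (soft tissue, pulmonary function). The tumor time-trend clause in 4.5 names DMH parameters only. Sections 4.4, 8.2 and 10.0 supply outcome data and modelled quantities. None states how performance would be measured or how DMH would be compared with DVH.

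**5. What a repair must measure.** Suppose the mass-weighted dose is a constant fraction c of the volume-weighted dose, m = c·v. A logistic model fitted to m is a + b·m = a + (b·c)·v, which is the model in v with a rescaled slope. The likelihoods and AUCs are identical, so refitted models and AUC show no difference. Under NTCP parameters fixed in advance, the probabilities at m and v do differ, and one set may lie closer to the observed rate. That is the benefit claimed in section 1.2.1, so discrimination alone is not enough.

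**6. Precision of an AUC comparison.** This bears only on the cost of the repair. The figures come from simulated binormal metrics with both AUCs 0.70, a fixed number of events and 20,000 replicates per setting. The half-width is 1.96 × the SD of the paired AUC difference.

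| Event rate | n per site (events) | r = 0.80 | r = 0.90 | r = 0.95 |
|---|---|---|---|---|
| 10% | 50 (5) | 0.165 | 0.120 | 0.087 |
| 10% | 100 (10) | 0.114 | 0.082 | 0.059 |
| 10% | 200 (20) | 0.080 | 0.057 | 0.041 |
| 20% | 50 (10) | 0.124 | 0.089 | 0.065 |
| 20% | 100 (20) | 0.086 | 0.062 | 0.045 |
| 20% | 200 (40) | 0.060 | 0.043 | 0.031 |
| 30% | 50 (15) | 0.107 | 0.079 | 0.057 |
| 30% | 100 (30) | 0.075 | 0.054 | 0.039 |
| 30% | 200 (60) | 0.052 | 0.037 | 0.027 |

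The AUC, the DVH–DMH correlation r, n and the 10% and 20% rates are assumptions. Only 30% comes from the protocol, as its background rate of symptomatic lung injury (section 1.2.1), and it applies to lung alone. Section 1.2.1 also reports a negligible DVH–DMH difference for PTV and spinal cord, so outside lung r may exceed 0.95.

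**The case against.** The strongest reply is that this is a non-therapeutic study that builds a database. Its objective is worded as study and evaluation, no treatment decision rests on the tests, and the outcome data are being gathered. Much of that stands, and it rules out several stronger readings.

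- A reader might infer that outcomes are not collected or that no link to outcome is intended. The documents say otherwise: sections 4.2 and 4.5 name both histograms against observed changes, section 4.4 brings in imaging that can show response and complications, and sections 8.2 and 10.0 record toxicity and follow-up.
- A reader might tally the outcome-related statements outside section 6.0 and score each as lacking a model or a comparison. That is too harsh. TCP and NTCP are models, though unspecified, and two of the statements do place DVH and DMH side by side. The missing parts are the metric and the test.
- A reader might take the sentence on imaging information in section 6.0 as a bar on outcome analysis. It explains why the planning comparisons are paired and does not limit what else may be analyzed.

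The reply does not remove the mismatch. The objective is labelled primary, and section 6.0 sets null hypotheses and thresholds and calls its analyses powered. Even an exploratory study needs one analysis aimed at its primary question.

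**Conclusion.** The point holds for the tests stated in section 6.0: 0 of 2 families take an observed outcome, and their results would be the same whether DMH predicts better than, worse than or as well as DVH. This follows from the text and rests on no assumed number. It is a mismatch between question and analysis, which goes beyond missing detail.

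It does not follow that the study's data could never answer the objective. No sample size is given, and the number and timing of toxicity assessments are not stated, so that remains open. The half-widths of about 0.03 to 0.17 rest wholly on the assumed n, AUC, correlation and event rates, apart from the lung-only 30%. They say only that small differences would probably not be resolved by site.

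**What to change.** Do one of the following.

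**Option 1: add an objective-1 analysis to section 6.0.**

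- Use the delivered plan and analyze by site.
- Fix one observed endpoint per site before outcomes are linked to dose: either a CTCAE 4.0 endpoint with grade cut-off and time window, or a named imaging or function measure with its time point. The objective is satisfied by response or complication, so toxicity alone can serve.
- Report calibration: DVH-based and DMH-based NTCP, under the same parameters fixed in advance, each against the observed rate.
- Report the paired difference in discrimination with a 95% confidence interval, for example the AUC of gEUD against that of mgEUD. Another paired measure would do.
- Label both as estimation, with no power claim.

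**Option 2: reword objective 1** as a dosimetric and modelled comparison.

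Option 1 costs section 6.0 wording, analysis time and a check that toxicity grades exist in the chosen window. That check matters: section 8.2 does not list toxicity among the items drawn from the record systems, and the Appendix I calendars have one follow-up column and no toxicity row. If the window fits existing records, no new visits or scans are needed. The other cost is wide intervals by site. Option 2 costs wording only, but it gives up the predictive question.
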